2. LIST OF ABBREVIATIONS

Term	Definition / description
AE	Adverse event
AESI	Adverse event of special interest
BI	Boehringer Ingelheim
BMI	Body mass index
CASA-Q	Cough and sputum assessment questionnaire
BRPM	Blinded report planning meeting
CF	Cystic fibrosis
CFQ-R	Cystic Fibrosis Questionnaire-Revised
CTP	Clinical Trial Protocol
CTR	Clinical Trial Report
CV	Arithmetic coefficient of variation
DBLM	Database lock meeting
ECG	Electrocardiogram
eCRF	Electronic case report form
EMA	European Medicines Agency
EudraCT	European union drug regulating authorities clinical trials
FEV ₁	Forced expiratory volume in 1 second
FEV ₁ % predicted	FEV ₁ percent predicted
gCV	Geometric coefficient of variation
gMean	Geometric mean
HR	Heart rate
ICH	International Council for Harmonisation of Technical Requirements for Pharmaceuticals for Human Use
IPD	Important protocol deviation
LCI	Lung clearance index
MBW	Multiple breath washout

Term	Definition / description
MedDRA	Medical Dictionary for Regulatory Activities
NOP	No peak detectable
PD	Pharmacodynamic(s)
PK	Pharmacokinetic(s)
PKS	PK analysis set
RS	Randomised set
SAE	Serious adverse event
SD	Standard deviation
SDL	Subject data listing
TEAE	Treatment emergent adverse event
TS	Treated set
TSAP	Trial statistical analysis plan

3. INTRODUCTION

As per ICH E9 ([10](#)), the purpose of this document is to provide a more technical and detailed elaboration of the principal features of the analysis described in the protocol, and to include detailed procedures for executing the statistical analysis of the primary and secondary variables and other data excluding interim analysis. Another TSAP document for the interim analysis is provided separately.

This TSAP assumes familiarity with the Clinical Trial Protocol (CTP), including Protocol Amendments. In particular, the TSAP is based on the planned analysis specification as written in CTP Section 7 “Statistical Methods and Determination of Sample Size”. Therefore, TSAP readers may consult the CTP for more background information on the study, e.g., on study objectives, study design and population, treatments, definition of measurements and variables, planning of sample size, randomization.

SAS® Version 9.4 will be used for all analyses. PK parameters will be calculated using Phoenix WinNonlin™ software (version Phoenix 6.3 or higher, Certara USA Inc., Princeton, NJ, USA).

4. CHANGES IN THE PLANNED ANALYSIS OF THE STUDY

The testing on the hypothesis of flat dose response curve that described in CTP will not be performed

In addition, model-based analysis of primary endpoint (trough FEV1 % predicted) and secondary endpoint (LCI),

For secondary endpoint (LCI), an analysis of covariance (ANCOVA) will be used to compare the change from baseline of LCI after 4 weeks of treatment. Other endpoints including patient reported outcomes (CASA-Q and CFQ-R) will be summarized descriptively for all dose levels.

age effect (adult versus adolescent) will be removed from the statistical model.

5. ENDPOINTS(S)

5.1 PRIMARY ENDPOINT(S)

The primary endpoint to assess efficacy of BI 1265162 200 µg bid over placebo is the absolute change from baseline in percent predicted trough Forced Expiratory Volume in 1 Second (FEV₁) after 4 weeks of treatment.

Trough FEV₁ is defined as measurement performed within 30 minutes prior to dosing.

Analysis is conducted using a restricted maximum likelihood (REML) based approach using a mixed model with repeated measurements (MMRM). Please refer to [Section 7.4.1](#) for details on the MMRM model.

Tables and/or spaghetti plots will display individual trough FEV₁ % predicted values over time and the change from baseline values overtime. In addition, a waterfall plot for change from baseline at Week 4 will be presented.

Baseline trough FEV₁ % predicted is defined as the last measurement taken on day 1 before first study drug administration.

5.2 SECONDARY ENDPOINT(S)

5.2.1 Key secondary endpoint(s)

Not applicable.

5.2.2 Secondary endpoint(s)

The secondary endpoints of this trial are:

- Change from baseline in Lung Clearance Index (LCI) assessed by N₂ Multiple Breath Washout (N₂MBW) procedure after 4 weeks of treatment
- Change from baseline in Cystic Fibrosis Questionnaire Revised (CFQ-R) total score after 4 weeks of treatment
- Change from baseline in Cough and Sputum Assessment Questionnaire (CASA-Q) (4 separate sub-scores) after 4 weeks of treatment
- Percentage of patients with treatment-emergent Adverse Events (AE) up to Day 36
- C_{t,N} (concentration of the analyte in plasma at time t following dose N)
- C_{pre,N} (predose concentration measured for dose N)

- $AUC_{0-t,N}$ (area under the concentration-time curve of the analyte in plasma until t hours after dose N)

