7.5.2.2 Safety endpoints

For analysis for AE, refer [Section 7.8.1](#).

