7.5.2.4 Analysis of Questionnaires (CASA-Q[©] and CFQ-R)

CASA-Q

The derivation of the CASA-Q domain scores will be performed according to the CASA-Q[©] user manual ([11](#)). All reported answers will be listed together with the derived domain scores.

Descriptive analysis will be done by treatment and domain score for baseline, Day 8, Day 29 and change from baseline.

CFQ-R

As no adolescent randomized, CFQ-R Teen/Adult version will be used.

The derivation of the CFQ-R scores will be performed according to the CFQ-R scoring instructions ([12](#)). The CFQ-R total score is the sum of each domain score. All reported answers will be listed together with the derived scores.

Descriptive analysis will be done by treatment and score for baseline, Day 29 and change from baseline and will be presented separately for total score and each domain score.

To explore the relationship between primary endpoint and CFQ-R respiratory domain score, a scatter plot of baseline CFQ-R respiratory domain score against change from baseline in FEV1 % predicted after 4 weeks of treatment.

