7.8 SAFETY ANALYSIS

All safety analyses will be performed on the treated set.

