7.8.1 Adverse Events

AEs will be coded with the most recent version of MedDRA.

The analyses of AEs will be descriptive in nature. All analyses of AEs will be based on the number of subjects with AEs and not on the number of AEs.

The analysis of AEs will be based on the concept of treatment emergent AEs. That means that all AEs occurring between first drug intake till 7 days after last drug intake will be assigned to the randomised treatment. All AEs occurring before first drug intake will be assigned to 'screening' and all AEs occurring after last drug intake + 7 days will be assigned to 'follow-up' (for listings only).

An overall summary of AEs will be presented. This overall summary will comprise summary statistics for the class of other significant AEs according to ICH E3 and for the class of adverse events of special interest (AESI). For the definition of AESI please refer to Section 5.2.6.1.4 of the CTP.

The frequency of subjects with AEs will be summarised by treatment (dose), primary system organ class and preferred term. AEs which were considered by the investigator to be drug related will be summarised separately. Separate tables will also be provided for subjects with serious AEs (SAEs), subjects with AESIs and subjects with other significant AEs (according to ICH E3). AEs will also be summarized by maximum intensity.

The system organ classes will be sorted according to the standard sort order specified by the European Medicines Agency (EMA), preferred terms will be sorted by total frequency (within system organ class).

A further table will present AEs by preferred term, dose group and intensity, sorted by descending relative frequency in any dose group.

Adverse events ongoing at Visits 2 (baseline), 3 (week 1) and 4 (week 4) will be provided to help explaining outliers regarding efficacy.

For disclosure of AE data on ClinicalTrials.gov, the frequency of subjects with non-serious AEs occurring with an incidence of greater than 5 % (in preferred terms) will be summarised by treatment, primary system organ class and preferred term. The frequency of subjects with SAEs will also be summarised.

For disclosure of AE data in the European union drug regulating authorities clinical trials (EudraCT) register, the frequency of AEs, the frequency of non-serious AEs with an incidence of greater than 5 % (in preferred terms) and the frequency of SAEs will be summarised.

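### Does the treatment-emergent AE percentage need a fixed count to Day 36 for patients who stop treatment early?

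*SAP*

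**What the plan says.** Section 5.2.2 of the SAP lists the safety endpoint as "Percentage of patients with treatment-emergent Adverse Events (AE) up to Day 36". Section 7.5.2.2 adds only a pointer ("For analysis for AE, refer" Section 7.8.1).

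Section 7.8.1 sets the counting rule. It opens with "The analysis of AEs will be based on the concept of treatment emergent AEs" and explains that "all AEs occurring between first drug intake till 7 days after last drug intake will be assigned to the randomised treatment". Beyond that limit, "all AEs occurring after last drug intake + 7 days will be assigned to 'follow-up' (for listings only". The same section counts subjects with an AE rather than events, and states "The analyses of AEs will be descriptive in nature".

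The denominator comes from Section 7.8 ("All safety analyses will be performed on the treated set") and from Section 7, which bases percentages on everyone in the analysis set. The end of the 4-week period is visible in Section 7.5.2.4, where the last CASA-Q assessment is Day 29: "Descriptive analysis will be done by treatment and domain score for baseline, Day 8, Day 29 and change from baseline".

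The SAP does not say whether Day 36 is a separate fixed limit or the nominal end of the Section 7.8.1 window.

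**The concern.** One endpoint appears to have two end limits: a study day in Section 5.2.2 and a limit relative to each patient's last dose in Section 7.8.1. They agree only for a last dose on Day 29. For an earlier stop the window closes before Day 36; for a later last dose it closes after.

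Early stoppers stay in the denominator in full while their time at risk shrinks. If stopping differed between arms, crude percentages would rest on unequal follow-up, and the arm with more early stops could look safer than it is. A first AE more than 7 days after the last dose, but by Day 36, would appear in no summary table. At stake is whether the reported figure is the endpoint that Section 5.2.2 names, and whether it is tilted between arms.

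**Working it through.** **1. Reproduce Day 36.** Window end = day of last dose + 7 (Section 7.8.1). For a last dose on Day 29: 29 + 7 = 36, the figure in Section 5.2.2. That the last dose falls on Day 29 is an inference from the Day 29 assessment; a last dose on Day 28 would give Day 35, one day short.

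**2. The gap for other stop days.** Days not counted = 36 − (last-dose day + 7).

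| Last dose | Window ends | Days to Day 36 not counted |
|---|---|---|
| Day 8 | Day 15 | 21 |
| Day 15 | Day 22 | 14 |
| Day 22 | Day 29 | 7 |
| Day 29 | Day 36 | 0 |

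**3. Who is affected.** The endpoint counts patients, so one AE inside the window counts the patient in full. The two limits give a different answer for an early stopper only if the *first* AE on study drug falls after last dose + 7 days and by Day 36. A patient who stops because of an AE had it before the window closed, so the loss is 0.

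**4. Size under assumptions.** The SAP gives no AE or stopping rates. Assume a constant hazard of first AE, the same on and off drug, with a proportion p of patients having an AE by Day 36. Assume also that a fraction f of the arm stops on day s independently of AEs. Then

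- hazard λ = −ln(1 − p)/36
- chance that a stopper is counted = 1 − exp(−λ(s + 7))
- shortfall in the arm = f × [p − (1 − exp(−λ(s + 7)))]

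For p = 0.50, s = 8, f = 0.20: λ = ln 2/36; a stopper is counted with probability 1 − exp(−15 ln 2/36) = 0.251; the arm shows 0.8 × 0.50 + 0.2 × 0.251 = 0.450 instead of 0.50. That is 5.0 points, or 1.40 of 28 patients. The 28 is the planned size of the placebo and 200 µg arms (14 + 14, Section 6.1).

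Over p = 0.3 to 0.7, s = Day 8 to 22 and f = 5% to 20%:

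- smallest shortfall (p = 0.3, s = 22, f = 5%): 0.3 points, 0.07 of 28 patients
- largest shortfall (p = 0.7, s = 8, f = 20%): 6.1 points, 1.71 of 28 patients

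With 5% stopping in one arm and 20% in the other, the between-arm difference shifts by 0.15 × [p − (1 − exp(−λ(s + 7)))], which is 0.75 points (p = 0.3, s = 22) to 4.58 points (p = 0.7, s = 8).

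**5. The two sections side by side.** Section 5.2.2 does not promise a count of all AEs to Day 36. It restricts the endpoint to treatment-emergent events, and Section 7.8.1 is where the SAP says what those are. An AE more than 7 days after an early last dose is not treatment-emergent under this SAP, so leaving it out follows the named endpoint. Read this way, Day 36 is what the rule gives for a patient who completes treatment.

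**The case for a change.** The strongest case for a change is that the SAP is meant to be the more detailed document, and it never says which limit governs. Reading Day 36 as nominal is plausible but unwritten. Even on that reading a last dose after Day 29 leaves a mismatch: Section 7.8.1 counts past Day 36 and Section 5.2.2, taken literally, does not. Two programmers could build slightly different numerators, and one sentence would settle it.

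The ambiguity of wording stands. The claimed bias does not. The argument from drug-related stopping fits poorly with the calculation behind it: patients who stop because of an AE lose nothing, and the shortfall in the illustration arises only if stopping is unrelated to AEs and the hazard is as high off drug as on it. In that case the uncounted events are no different from background events. A difference between arms would also need unequal stopping, which the SAP gives no ground to assume.

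A fixed count to Day 36 would not be a plain correction either. It replaces an on-treatment question with a fixed-period one and brings in late events unrelated to treatment. It also needs AEs to be collected to Day 36 after early discontinuation, which the SAP does not state. If they are not, the count would be incomplete in just the patients it is meant to help.

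**Conclusion.** No change to the plan is needed. Following Section 7.8.1 as written gives a conventional treatment-emergent AE percentage, which agrees with Day 36 for a last dose on Day 29. Last dose plus a 7-day residual period is a legitimate counting rule, and an analyst sent from Section 7.5.2.2 to Section 7.8.1 would apply it without difficulty. A sentence linking the two sections would be tidy, but it would not alter the tables on that reading.

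Under the assumed ranges, the difference from a fixed Day 36 count is 0.3 to 6.1 points within an arm. The upper end requires a 70% AE rate and a fifth of the arm stopping as early as Day 8 for reasons unrelated to AEs, which is severe for a 4-week trial. No test or decision rule hangs on the percentage, and the events concerned remain in the listings.

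This conclusion rests on reading Day 36 as Day 29 + 7. If Day 36 was meant as a separate fixed limit, the figures above bound the difference for early stoppers under the same assumptions; a last dose after Day 29 would work the other way, adding one day of counting for each day of delay.

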6. GENERAL ANALYSIS DEFINITIONS

6.1 TREATMENT(S)

For basic study information on treatments to be administered please refer to Section 4 of the CTP.

Patient randomisation will start with only adult patients to either 200 µg bid of BI 1265162 or placebo in a 1:1 ratio. Enrolment of adolescent patients will be based on periodic reviews of adult patient safety data. The analysis plan for periodic safety reviews of adult patients will be described separately.

As soon as 28 patients are allocated to these two treatment arms, the remaining patients will be allocated to the other doses of BI 1265162 as well as the highest dose and placebo in a 1:1:1:1:1 ratio (14 patients per treatment arm). As a result, it was planned to have patients distributed in a 2:1:1:1:2 ratio (2 for either placebo or 200 µg bid of BI 1265162 and 1 for other doses of BI 1265162) with around 20% of adolescents per group.

Patients will be analysed according to [Table 6.3: 1](#). All planned analysis will be presented by this treatment group, unless specified otherwise. Handling of patients where treatment assignment has not been followed will be handled on a case-by-case basis, to be agreed at report planning meetings or DBL meeting (but prior to database lock).

6.3 SUBJECT SETS ANALYSED

The statistical analysis will be based on the following analysis sets.

- Enrolled set (ES): This subject set includes subjects that signed informed consent and underwent screening procedures.
- Randomized set (RS): This subject set includes all randomised subjects, whether treated or not.

- Treated set (TS): The treated set includes all subjects who were randomized and treated with at least one dose of study drug. The treatment assignment will be determined based on the first treatment the subjects received.
- N₂ multiple breath washout set (N2MBWS): The N2MBWS includes all subjects in the treated set, who provided at least one pair (baseline and end of treatment) of evaluable measures of the N2MBW parameter.
- Pharmacokinetic set (PKS): The PK parameter analysis set (PKS) includes all subjects in the Treated Set (TS) who provide at least one PK parameter that was not excluded according to the description in Section 7.3.5 of the CTP. Excluded subjects will be listed with their individual plasma concentrations and individual pharmacokinetic parameters, however, will not be included in descriptive statistics for plasma concentrations, pharmacokinetic parameters or other statistical assessment.

Table 6.3: 1 Analysis Sets

Class of endpoint	Analysis Set				
	ES	RS	TS	PKS	N2MBWS
Disposition	X				
Exposure			X		
iPDs		X			
Demographic/baseline endpoints			X		
Safety endpoints			X		
Secondary PK endpoints				X	
Efficacy endpoints based on N ₂ MBW measurements (LCI,					X
Efficacy endpoints from pulmonary function tests			X		
CASA-Q, CFQ-R			X		

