7. PLANNED ANALYSIS

The format of the listings and tables will follow the BI guideline "Reporting of clinical trials and project summaries" ([7](#)).

The individual values of all subjects will be listed, sorted by treatment group, subject number and visit (if visit is applicable in the respective listing). AE listings will be sorted by assigned treatment (see [Section 7.8.1](#) below for details). The listings will be contained in Appendix 16.2 subject data listings (SDL) of the CTR.

Inferential statistical analyses of PK NCA endpoints will be presented in Section 15.5 of the CTR and in Appendix 16.1.9.3.

Descriptive data analysis of PK NCA endpoints will be presented in Section 15.6 of the CTR.

The following standard descriptive statistical parameters will be displayed in summary tables of continuous variables:

N	number of non-missing observations
Mean	arithmetic mean
SD	standard deviation
Min	minimum
Median	median
Max	maximum

For scores derived from questionnaire data, the following descriptive statistics will be calculated:

N	number of non-missing observations
Mean	arithmetic mean
SD	standard deviation

For plasma concentrations as well as for all PK parameters, the following descriptive statistics will additionally be calculated:

CV	arithmetic coefficient of variation
gMean	geometric mean
gCV	geometric coefficient of variation

The data format for descriptive statistics of plasma concentrations will be identical with the data format of the respective concentrations. The descriptive statistics of PK parameters will be calculated using the individual values with the number of decimal places as provided by the evaluation program. Then the individual values as well as the descriptive statistics will be reported with three significant digits in the CTR.

Tabulations of frequencies for categorical data will include all possible categories and will display the number of observations in a category as well as the percentage (%) relative to the respective treatment group. Percentages will be rounded to one decimal place. The category

missing will be displayed only if there are actually missing values. Percentages will be based on all subjects in the respective analysis set whether they have non-missing values or not.

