7.4.1 Primary analysis of the primary endpoint(s)

To account for the repeated nature of the data and the covariates in the nature, a restricted maximum likelihood (REML) based approach using a mixed model with repeated measurements (MMRM) will be carried out comparing the change from baseline in percent predicted trough FEV1 percent predicted at 4 weeks of treatment.

The analysis will include the fixed, categorical effects of treatment at each visit and the fixed continuous effects of baseline at each visit. Visit will be treated as the repeated measure with an unstructured covariance structure used to model the within-patient measurements. The model will only include data from highest dose level and placebo because of limited sample size from other dose levels.

The Kenward-Roger approximation will be used to estimate denominator degrees of freedom and adjust standard errors.

The MMRM analysis will be carried out in SAS and covariate-adjusted fixed effect estimates of average response for each dose group and the covariance matrix will be extracted from the fit.

The following SAS[®] code for MMRM will be used:

```
PROC MIXED DATA=alldata cl method=reml ocovtest;
  CLASS usubjid trtpso avisitn;
  MODEL ept = trtpso*avistin base*avistin /ddfm=kr solution;
  REPEATED avisitn /subject=usubjid type UN r rcorr;
  LSMEANS trtpso*avistin / pdiff=all om cl alpha=0.05;
RUN;
```

If the model failed to converge, the following covariance structures will be tested in order: UN → AR(1).

For subgroup analysis, same MMRM model will be carried out within each subgroup.

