7.5.2 Secondary endpoint(s)

7.5.2.1 Analysis of LCI

An analysis of covariance (ANCOVA) will be used to compare the change from baseline of LCI after 4 weeks of treatment with adjustment for categorical effects of treatment and the fixed continuous effect of baseline. The model will include data from highest dose level and placebo. Descriptive analysis will be performed for other dose levels.

Tables and/or spaghetti plots will display individual LCI values over time. In addition, a waterfall plot for change from baseline at Week 4 will be presented.

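### The SAP groups a mis-dosed patient by first treatment received, which takes that patient out of the randomised arm in the FEV1 and LCI comparisons, while Section 7.8.1 states the opposite rule for adverse events

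*SAP*

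**What the plan says.** Four parts of the SAP bear on a patient whose first treatment received differs from the randomised one.

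- **Section 6.3, Treated set:** "The treatment assignment will be determined based on the first treatment the subjects received". Table 6.3: 1 assigns the pulmonary function endpoints, CASA-Q, CFQ-R and safety to this set. LCI is assigned to the N2MBWS, which Section 6.3 defines as a subset of it.
- **Sections 7.4.1 and 7.5.2.1, the two models:** for FEV1, "The model will only include data from highest dose level and placebo"; for LCI, "The model will include data from highest dose level and placebo". Both refer to treatment without further qualification.
- **Sections 7.8 and 7.8.1, safety:** "All safety analyses will be performed on the treated set", but "all AEs occurring between first drug intake till 7 days after last drug intake will be assigned to the randomised treatment". Section 7 adds "AE listings will be sorted by assigned treatment" and refers to 7.8.1 for details.
- **Section 6.1:** "Handling of patients where treatment assignment has not been followed will be handled on a case-by-case basis", to be settled before the database is locked.

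**The concern.** There are two separate problems.

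For efficacy, the only grouping rule in the visible text is first treatment received. A comparison is protected by randomisation only if patients are counted in the arm to which they were randomised. The rule also looks only at the first treatment. A patient given the wrong first dose and the correct treatment for the rest of the 4 weeks would still be counted in the other arm at Week 4. That grouping reflects neither the randomisation nor the treatment mostly taken.

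For adverse events, two stated rules give different arms for the same patient. This touches a listed secondary endpoint, the percentage of patients with treatment-emergent adverse events. The terms add to the difficulty: Section 6.3 uses treatment assignment to mean first treatment received, whereas Section 7 uses assigned treatment and refers to a section that says randomised.

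Section 6.1 covers the same patients but does not say whether its decision replaces the rules in 6.3 and 7.8.1. If a mis-dosing occurred, the arm would be chosen after the event was known.

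**Working it through.** **Step 1: which rule applies to which endpoint**

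| Endpoint | Analysis set | Grouping that follows for a mis-dosed patient |
|---|---|---|
| FEV1 (primary) | Treated set | First treatment received (6.3) |
| LCI | N2MBWS, within the Treated set | First treatment received (6.3, through the subset) |
| CFQ-R, CASA-Q | Treated set | First treatment received (6.3) |
| PK | PKS, within the Treated set | First treatment received (6.3, through the subset) |
| Adverse events | Treated set | First treatment received (6.3, 7.8) and randomised treatment (7.8.1) |

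The direct contradiction is confined to adverse events. For efficacy there is one rule, and the question is whether it is a good one.

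**Step 2: arm size**

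The SAP gives no figure for this effect, so there is none to reproduce. Section 6.1 plans 28 patients randomised 1:1 to 200 µg and placebo, which is 14 per arm, and then 14 in each of five arms. The planned size of each primary arm is therefore n = 14 + 14 = 28, which agrees with the stated 2:1:1:1:2 ratio (28:14:14:14:28). Actual arm sizes are not given. As an assumed lower bound, n = 14 covers the first stage only. One patient is 1/28 = 3.6% of an arm as planned, or 1/14 = 7.1% at the lower bound.

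**Step 3: effect of one mis-dosed patient on the difference in means**

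Suppose one patient with value x is randomised to placebo but first receives 200 µg. Let mP be the mean of the other n − 1 placebo patients and mA the mean of the n patients randomised to 200 µg.

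- By randomised treatment: mA − mP − (x − mP)/n
- By first treatment received: mA − mP + (x − mA)/(n + 1)
- Change from the first to the second: (x − mA)/(n + 1) + (x − mP)/n

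Two cases, as a percentage of mA − mP:

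| Patient responds like | Change | n = 28 | n = 14 (assumed) |
|---|---|---|---|
| the 200 µg mean (x = mA) | +1/n | +1/28 = +3.6% | +1/14 = +7.1% |
| the placebo mean (x = mP), for example if only the first dose was wrong | −1/(n + 1) | −1/29 = −3.4% | −1/15 = −6.7% |

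The sign depends on the kind of dosing error, so neither grouping is always the conservative one. These are unadjusted means, not MMRM or ANCOVA estimates.

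**The case against.** The strongest reply is that the efficacy grouping is stated and consistent. Section 6.1 says patients are analysed according to Table 6.3: 1, and a general definition need not be repeated in each model section. This stands. A reader might infer from the unqualified treatment term in "MODEL ept = trtpso*avistin base*avistin /ddfm=kr solution", and from the undefined variable trtpso, that the SAP leaves the efficacy grouping open. It does not: the rule in 6.3 reaches both models through the table. An undefined variable name is missing detail and contradicts nothing. What remains is an objection to the rule itself.

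On adverse events, the sentence in 7.8.1 mainly separates screening, treatment and follow-up, so the word randomised may be a slip. It could also be read as a specific exception, since 6.1 allows departures where specified. Either reading is possible, but the text does not say which is meant. A reader might go further and infer that an event and the patient's place in the denominator would fall in different arms. No section calls for that split, and 7.8.1 counts patients, not events.

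Section 6.1 does provide a route for these patients, decided before lock. That limits the harm but sets no order among the rules. A reader might also infer an unblinded decision, because the database lock meeting is allowed and no blinding is stated for it. That is an inference from silence: Section 2 defines a blinded report planning meeting, and blinding is commonly left to the protocol. Section 6.2, with its table on handling important protocol deviations, is not shown and may also bear on such patients.

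**Conclusion.** The point holds, and it is minor. Section 6.3 sets a rule that takes a mis-dosed patient out of the randomised arm for the primary and LCI comparisons, even if only the first dose was wrong. Section 7.8.1 states a different rule for adverse events on the same analysis set, and 6.1 does not say which prevails.

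The size is contingent. It is zero if every patient's first treatment was the randomised one, and nothing in the SAP suggests otherwise. For one mis-dosed patient, the choice of grouping moves the unadjusted difference by about 3.4% to 3.6% in either direction at the planned 28 per arm, or 6.7% to 7.1% at an assumed 14. This supposes that the patient responds like one arm mean or the other. The material does not support a claim that the primary result is biased or that any misallocation took place.

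**What to change.** - **Section 6.3:** state that the efficacy endpoints (FEV1, LCI, CFQ-R, CASA-Q) are grouped by randomised treatment, and that safety and PK are grouped by first treatment received.
- **Section 7.8.1:** replace the reference to randomised treatment with the first-treatment-received rule. Use the same term for the adverse event listings in Section 7.
- **Section 6.1:** limit the case-by-case clause to situations that these rules do not cover.

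The changes to 7.8.1 and Section 7 are wording. The efficacy change in 6.3 reverses the rule now stated and should be recorded as a change to the analysis, made before lock. None of it needs new data or patients, and results are unaffected if no patient was mis-dosed.
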